6.6. Dose Modification

Dose modification of PF-07923568 is not allowed.

6.7. Continued Access to Study Intervention After the End of the Study

No study intervention will be provided to participants at the end of their study participation.

6.8. Treatment of Overdose

For this study, any dose of PF-07923568 greater than 1200 mg within a 24-hour time period will be considered an overdose.

There is no specific treatment for an overdose.

In the event of an overdose, the investigator/treating physician should:

1. Contact the study medical monitor within 24 hrs.
2. Closely monitor the participant for any AEs/SAEs and laboratory abnormalities as medically appropriate and at least until the next scheduled follow-up.
3. Document the quantity of the excess dose as well as the duration of the overdose in the CRF.
4. Overdose is reportable to Pfizer Safety only when associated with an SAE.
5. Obtain a blood sample for PK analysis within 3 days from the date of the last dose of study intervention if requested by the study medical monitor (determined on a case-by-case basis).

6.9. Prior and Concomitant Therapy

All concomitant treatments taken during the study must be recorded with indication, daily dose, and start and stop dates of administration. All participants will be questioned about concomitant treatment at each clinic visit.

Treatments taken within 28 days before study intervention dosing on Day 1 will be documented as a prior treatment. Treatments taken after the first dose of study intervention will be documented as concomitant treatments.

Females using hormonal contraceptives or taking hormone replacement therapy are eligible to participate in this study. See [Appendix 4](#) for hormonal contraceptives that are permitted in this study.

Participants on certain medications are **excluded** from the study (see [Appendix 9](#) for list of prohibited medications due to potential drug-drug interaction).

Sites are encouraged to contact the sponsor should there be questions as to whether a medication is permitted or prohibited.

6.9.1. Participants in Group 1 Only (without Hepatic impairment)

In general, participants in Group 1 (without HI) will abstain from all concomitant treatments, except for the treatment of AEs. Of note, are the following **restrictions**:

- Acetaminophen/paracetamol may be used at doses of ≤ 1 g/day;
- Herbal supplements must be discontinued ***at least 28 days prior*** to Day 1 and until the follow-up;
- Limited use of prescription and nonprescription medications that are not believed to affect the overall results of the study may be permitted on **a case-by-case basis after approval** from the sponsor study team.

6.9.2. Participants in Groups 2-4 Only (Hepatic Impairment)

Participants in Groups 2-4 (with HI) are permitted to be on stable doses of background medications for the management of their concomitant medical condition(s), as long as this is in line with protocol specifications regarding prohibited medications as described above in [Section 6.9](#) and in [Appendix 9](#). On a ***case-by-case basis***, with approval from the sponsor, participants receiving fluctuating concomitant medication/treatment may be considered if the underlying disease is under control. **Whenever possible**, attempts must be made to **not** add new medications or alter the doses and regimens of the concomitant medications after enrollment and for the duration of participation in this study, except in circumstances where a change is deemed medically necessary. Any changes must be captured in the CRF.

Participants may receive any permitted background medications according to their stable medication routine at their usual dosing times. This is with the exception of phosphate binders, antacids, and bile acid binding resins (eg, cholestyramine, colestipol), which must not be administered within the 8 hrs before study intervention dosing or within the 4 hrs after study intervention dosing on Day 1. **On Day 1**, the investigator will determine the appropriate time to administer medications that are to be taken on an empty stomach. Otherwise, permitted concomitant medications that may be administered under fed conditions can be taken with breakfast on the morning of Day 1. On all other study days, participants are to receive their background medications at their usual times.

6.9.3. Rescue Medicine

There is no rescue therapy to reverse AEs observed with PF-07923568; standard medical supportive care must be provided to manage any AEs.

7. DISCONTINUATION OF STUDY INTERVENTION AND PARTICIPANT DISCONTINUATION/WITHDRAWAL

7.1. Discontinuation of Study Intervention

Since this is a single-dose study, this section is NA.

7.2. Participant Discontinuation/Withdrawal from the Study

A participant may withdraw from the study at any time at their own request. Reasons for discontinuation from the study include the following: safety, behavioral, compliance or administrative reasons, or if the study is terminated by sponsor.

At the time of discontinuing from the study, if possible, an early discontinuation visit should be conducted. See the [SoA](#) for assessments to be collected at the time of study discontinuation and follow-up and for any further evaluations that need to be completed.

The early discontinuation visit applies only to participants who are enrolled and then are prematurely withdrawn from the study. Participants should be questioned regarding their reason for withdrawal. The participant will be permanently discontinued from the study intervention and the study at that time.

If a participant withdraws from the study, they may request destruction of any remaining samples taken and not tested, and the investigator must document any such requests in the site study records and notify the sponsor accordingly.

If the participant withdraws from the study and also withdraws consent (see Section 7.2.1) for disclosure of future information, no further evaluations will be performed and no additional data will be collected. The sponsor may retain and continue to use any data collected before such withdrawal of consent.

7.2.1. Withdrawal of Consent

Participants who request to discontinue receipt of study intervention will remain in the study and must continue to be followed for protocol-specified follow-up procedures. The only exception to this is when a participant specifically withdraws consent for any further contact with them or persons previously authorized by the participant to provide this information. Participants should notify the investigator in writing of the decision to withdraw consent from future follow-up, whenever possible. The withdrawal of consent should be explained in detail in the medical records by the investigator, as to whether the withdrawal is only from further receipt of study intervention or also from study procedures and/or post-treatment study follow-up, and entered on the appropriate CRF page. In the event that vital status (whether the participant is alive or dead) is being measured, publicly available information should be used to determine vital status only as appropriately directed in accordance with local law.

7.3. Lost to Follow-up

A participant will be considered lost to follow-up if the participant repeatedly fails to return for scheduled visits and is unable to be contacted by the study site.

The following actions must be taken if a participant fails to attend a required study visit:

- The site must attempt to contact the participant and reschedule the missed visit as soon as possible. Counsel the participant on the importance of maintaining the assigned visit schedule and ascertain whether the participant wishes to and/or should continue in the study;
- Before a participant is deemed lost to follow-up, the investigator or designee must make every effort to regain contact with the participant (where possible, 3 telephone calls and, if necessary, a certified letter to the participant's last known mailing address or local equivalent methods). These contact attempts should be documented in the participant's medical record;
- Should the participant continue to be unreachable, the participant will be considered to have withdrawn from the study.

8. STUDY ASSESSMENTS AND PROCEDURES

8.1. Administrative Procedures

The investigator (or an appropriate delegate at the investigator site) must obtain a signed and dated ICD before performing any study-specific procedures.

Study procedures and their timing are summarized in the [SoA](#). Protocol waivers or exemptions are not allowed.

Adherence to the study design requirements, including those specified in the [SoA](#), is essential and required for study conduct.

All screening evaluations must be completed and reviewed to confirm that potential participants meet all eligibility criteria. The investigator will maintain a screening log to record details of all participants screened and to confirm eligibility or record reasons for screening failure, as applicable.

Participants will be screened within 28 days prior to administration of the study intervention to confirm that they meet the study population criteria for the study. If the time between screening and dosing exceeds 28 days as a result of unexpected delays (eg, delayed drug shipment), then participants may be rescreened after contact with a sponsor Clinical representative as described in [Section 5.4](#).

Every effort should be made to ensure that protocol-required tests and procedures are completed as described. However, it is anticipated that from time to time there may be circumstances outside the control of the investigator that make it unfeasible to perform the test. In these cases, the investigator must take all steps necessary to ensure the safety and well-being of the participant. When a protocol-required test cannot be performed, the investigator will document the reason for the missed test and any corrective and preventive actions that they have taken to ensure that required processes are adhered to as soon as possible. The study team must be informed of these incidents in a timely manner.

If done around the time of a blood draw, ECGs and vital sign assessments (BP and pulse rate) should be collected before the blood draw. If an IV catheter is utilized for blood sample collections, ECGs and vital sign assessments (BP and pulse rate) should be collected before insertion of the catheter.

For samples being collected and shipped, detailed collection, processing, storage, and shipment instructions and contact information will be provided to the investigator site prior to initiation of the study.

The total blood sampling volume for individual participants in this study is approximately 95 mL. The actual collection times of blood sampling may change. Additional blood samples may be taken for safety assessments at times specified by Pfizer, provided the total volume taken during the study does not exceed 550 mL during any period of 56 consecutive days.

To prepare for study participation, participants will be instructed on the information in the [Lifestyle Considerations](#) and [Concomitant Therapy](#) sections of the protocol.

8.2. Efficacy Assessments

NA.

8.3. Safety Assessments

Planned time points for all safety assessments are provided in the [SoA](#). Unscheduled safety measurements may be obtained at any time during the study to assess any perceived safety issues.

8.3.1. Physical Examinations

A complete PE will include, at a minimum, head, ears, eyes, nose, mouth, neck, skin, heart and lung examinations, lymph nodes, and gastrointestinal, musculoskeletal, and neurological systems.

A limited PE will include, at a minimum, assessments of general appearance, the respiratory and cardiovascular systems, and participant-reported symptoms.

PEs may be conducted by a physician, trained physician's assistant, or nurse practitioner as acceptable according to local regulation.

Height and weight will also be measured per the [SoA](#) and recorded in the CRF. For measuring weight, a scale with appropriate range and resolution is used and must be placed on a stable, flat surface. Participants must remove shoes, bulky layers of clothing, and jackets so that only light clothing remains. They must also remove the contents of their pockets and remain still during measurement of weight.

PE findings collected during the study will be considered source data and will not be required to be reported, unless otherwise noted. Any untoward PE findings that are identified during the active collection period and meet the definition of an AE or SAE ([Appendix 3](#)) must be reported according to the processes in [Section 8.4.1](#) to [8.4.3](#).

8.3.2. Vital Signs

8.3.2.1. Blood Pressure and Pulse Rate

BP and pulse rate will be measured as defined in the [SoA](#).

- **Single, seated** BP and pulse rate will be measured with the participant's arm supported at the level of the heart, and recorded to the nearest mmHg, following a rest of **≥5 minutes**;
- Same arm (preferably the dominant arm) will be used for BP/pulse rate assessment throughout the study;
- BP/pulse rate assessment should not be taken from the arm with an IV catheter, if placed;
- Participants should be instructed not to speak during BP/pulse rate measurements.

The same properly sized and calibrated BP cuff will be used to measure BP each time. The use of an automated device for measuring BP and pulse rate is acceptable; however, when done manually, pulse rate will be measured in the brachial/radial artery for at least 30 seconds. When the timing of these measurements coincides with a blood collection, BP and pulse rate should be obtained prior to the nominal time of the blood collection.

Additional collection times, or changes to collection times, of BP and pulse rate will be permitted, as necessary, to ensure appropriate collection of safety data.

Any untoward vital sign findings that are identified during the active collection period and meet the definition of an AE or SAE ([Appendix 3](#)) must be reported according to the processes in [Section 8.4.1](#) to [8.4.3](#).

8.3.3. Electrocardiograms

Single, supine standard 12-lead ECGs utilizing limb leads (with a 10-second rhythm strip) should be collected at times specified in the **SoA** section of this protocol using an ECG machine that automatically calculates the HR and measures PR interval, QT interval, QTcF, and QRS complex. Alternative lead placement methodology using torso leads (eg, Mason-Likar) should not be used given the potential risk of discrepancies with ECGs acquired using standard limb lead placement. All scheduled ECGs should be performed after the participant has rested quietly for at least 5 minutes in a supine position.

To ensure safety of the participants, a qualified individual at the investigator site will make comparisons to baseline measurements. Additional ECG monitoring will occur if a) a post-dose QTcF interval is increased by ≥ 60 ms from the baseline **and** is >450 ms; or b) an absolute QT value is ≥ 500 ms for any scheduled ECG. If either of these conditions occurs, then 2 additional ECGs will be collected approximately 2 to 4 minutes apart to confirm the original measurement. If the QTcF values from these repeated ECGs remain above the threshold value, then a single ECG must be repeated at least hourly until QTc values from 2 successive ECGs fall below the threshold value that triggered the repeat measurement.

If a) a post-dose QTcF interval remains ≥ 60 ms from the baseline **and** is >450 ms; or b) an absolute QT value is ≥ 500 ms for any scheduled ECG for greater than 4 hours (or sooner, at the discretion of the investigator); or c) QTcF value get progressively longer, the participant should undergo continuous ECG monitoring. A cardiologist should be consulted if QTcF values do not return to less than the criteria listed above after 8 hrs of monitoring (or sooner, at the discretion of the investigator).

In some cases, it may be appropriate to repeat abnormal ECGs to rule out improper lead placement as contributing to the ECG abnormality. It is important that leads be placed in the same positions each time in order to achieve precise ECG recordings. If a machine-read QTc value is prolonged, as defined above, repeat measurements may not be necessary if a qualified medical provider's interpretation determines that the QTcF values are in the acceptable range.

ECG values of potential clinical concern are listed in [Appendix 8](#).

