9.3.3.1. Electrocardiogram Analyses

Changes from baseline for the ECG parameters HR, QTcF, PR interval, and QRS complex will be summarized by treatment and time. The frequency of uncorrected QT values above 500 ms will be tabulated.

The number (%) of participants with maximum post-dose QTcF values and maximum increases from baseline in the following categories will be tabulated by treatment:

Safety QTcF Assessment

| Degree of Prolongation | Mild (ms) | Moderate (ms) | Severe (ms) |
|-------------------------------|------------------|----------------------|--------------------|
| Absolute value | >450-480 | >480-500 | >500 |
| Increase from baseline | | 30-60 | >60 |

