10.8. Appendix 8: ECG Findings of Potential Clinical Concern

| ECG Findings That May Qualify as AEs |
|---|
| 
Marked sinus bradycardia (rate <40 bpm) lasting minutes.New PR interval prolongation >280 ms.New prolongation of QTcF to >480 ms (absolute) or by \geq60 ms from baseline.New-onset atrial flutter or fibrillation, with controlled ventricular response rate: ie, rate <120 bpm.New-onset type I second-degree (Wenckebach) AV block of >30 seconds' duration.Frequent PVCs, triplets, or short intervals (<30 seconds) of consecutive ventricular complexes. |
| ECG Findings That May Qualify as SAEs |
| 
QTcF prolongation >500 ms.New ST-T changes suggestive of myocardial ischemia.New-onset LBBB (QRS complex >120 ms).Newonset right bundle branch block (QRS complex >120 ms).Symptomatic bradycardia.Asystole:
In awake, symptom-free participants in sinus rhythm, with documented periods of asystole \geq3.0 seconds or any escape rate <40 bpm, or with an escape rhythm that is below the AV node.In awake, symptom-free participants with atrial fibrillation and bradycardia with 1 or more pauses of at least 5 seconds or longer.Atrial flutter or fibrillation, with rapid ventricular response rate: rapid = rate >120 bpm.Sustained supraventricular tachycardia (rate >120 bpm) ("sustained" = short duration with relevant symptoms or lasting >1 minute). |

- Ventricular rhythms >30 seconds' duration, including idioventricular rhythm (HR <40 bpm), accelerated idioventricular rhythm (HR >40 bpm to <100 bpm), and monomorphic/polymorphic ventricular tachycardia (HR >100 bpm [such as torsades de pointes]).
- Type II second-degree (Mobitz II) AV block.
- Complete (third-degree) heart block.

ECG Findings That Qualify as SAEs

- Change in pattern suggestive of new myocardial infarction.
- Sustained ventricular tachyarrhythmias (>30 seconds' duration).
- Second- or third-degree AV block requiring pacemaker placement.
- Asystolic pauses requiring pacemaker placement.
- Atrial flutter or fibrillation with rapid ventricular response requiring cardioversion.
- Ventricular fibrillation/flutter.
- At the discretion of the investigator, any arrhythmia classified as an adverse experience.

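### Protocol 8.3.3 has no absolute QTcF trigger for repeat ECGs, so some post-dose QTcF values above 500 ms call for no protocol-required repeat

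*Protocol*

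**What the plan says.** Protocol 8.3.3 sets two triggers for two further ECGs. Limb (a) needs both a post-dose QTcF rise of at least 60 ms and a QTcF above 450 ms. Limb (b) applies if "an absolute QT value is" 500 ms or more. The same section lists QT and QTcF as separate machine outputs.

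The later steps mostly use the corrected interval:

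- Confirmation, leading to hourly ECGs: "If the QTcF values from these repeated ECGs remain above the threshold value".
- Stopping: hourly ECGs run "until QTc values from 2 successive ECGs fall below the threshold value that triggered the repeat measurement".
- Continuous monitoring: limbs (a) and (b) again, if persistent, plus a limb (c), "QTcF value get progressively longer, the participant should undergo continuous ECG monitoring".
- Cardiology: "A cardiologist should be consulted if QTcF values do not return to less than the criteria listed above".

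A closing sentence lets a qualified provider's over-read of QTcF make repeats unnecessary.

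Protocol 9.3.3.1 tabulates "maximum post-dose QTcF values and maximum increases from baseline" by category, with QTcF above 500 ms as Severe. It adds a separate line for the other interval: "The frequency of uncorrected QT values above 500 ms will be tabulated". Appendix 8 (10.8) lists QTcF above 500 ms as a finding that may qualify as an SAE.

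The screening QTcF ceilings are 450 ms for Group 1 (5.2.2, item 3) and 470 ms for Groups 2-4 (5.2.3, item 7).

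**The concern.** The protocol treats QTcF above 500 ms as its most serious grade of prolongation, yet the rule that orders repeat ECGs does not use that limit. A participant who starts with a fairly long QTcF can pass 500 ms on a rise too small for limb (a). Limb (b) then helps only if the uncorrected QT also reaches 500 ms, which depends on heart rate. Above 60 bpm, QT is shorter than QTcF, so limb (b) can stay silent.

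What is at stake is an automatic repeat ECG at a value the protocol calls Severe, in a study whose stated cardiovascular mitigation (2.3.1) includes ECG assessment. The room for this is larger in the impaired groups because their entry ceiling is higher.

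**Working it through.** The plan gives no figure to reproduce. The check applies the two limbs as written.

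**Inputs**

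- Limbs (a) and (b): Protocol 8.3.3.
- Entry ceilings of 450 and 470 ms: Protocol 5.2.2 and 5.2.3.
- QTcF = QT/(60/HR)^(1/3), and baseline = Day 1 predose: SAP 3.5.4.

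**Step 1: when limb (a) is silent.** It is silent if post-dose QTcF is below baseline + 60. For this to leave room above 500 ms, baseline must exceed 500 - 60 = 440 ms. The width of the room is baseline - 440.

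**Step 2: when limb (b) is silent.** QT = QTcF x (60/HR)^(1/3) is below 500 ms when HR > 60 x (QTcF/500)^3.

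| Post-dose QTcF (ms) | Limb (b) silent above (bpm) |
|---|---|
| 501 | 60.4 |
| 505 | 61.8 |
| 510 | 63.7 |
| 520 | 67.5 |
| 529 | 71.1 |

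**Step 3: both limbs together.** Whole-millisecond QTcF values above 500 that fire neither limb:

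| Baseline (ms) | Width from step 1 (ms) | At 60 bpm | At 65 bpm | At 75 bpm |
|---|---|---|---|---|
| 440 | 0 | none | none | none |
| 445 | 5 | none | 501-504 | 501-504 |
| 450 (Group 1 ceiling) | 10 | none | 501-509 | 501-509 |
| 460 | 20 | none | 501-513 | 501-519 |
| 470 (Groups 2-4 ceiling) | 30 | none | 501-513 | 501-529 |

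In whole milliseconds the first affected baseline is 442: QTcF 501 is then a rise of 59. At 65 bpm, limb (b) takes over once QTcF passes 500/(60/65)^(1/3) = 513.5 ms.

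**Step 4: examples.**

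- Baseline 455, post-dose QTcF 510, 70 bpm: QT = 510 x (60/70)^(1/3) = 484.5 ms; rise = 510 - 455 = 55 ms. Neither limb fires.
- Baseline 470, post-dose QTcF 529, 75 bpm: QT = 529 x (60/75)^(1/3) = 491.1 ms; rise = 59 ms. Neither limb fires. At 70 bpm the QT would be 502.5 ms and limb (b) would fire.

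With a limb for QTcF of at least 500 ms, both examples trigger, as does every value in the step 3 table.

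**Step 5: slow heart rates.** Below 60 bpm the relation reverses. At 50 bpm, QT 510 ms is QTcF 479.9 ms, and QT must reach 531.3 ms before QTcF reaches 500 ms. At 45 bpm, QT 500 ms is QTcF 454.3 ms. These figures bear on how a limb (b) alert is confirmed and on why the QT limb should be kept.

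**The case against.** **QT in limb (b) may be a slip for QTc.** The confirmation, stopping and cardiology sentences, and the over-read sentence, all speak as if the thresholds were corrected ones. If QTc was meant, the window closes. This is a fair reading of intent, but the text does not say it. Section 8.3.3 names QT and QTcF separately, 9.3.3.1 shows that the protocol also has a use for uncorrected QT, and sites must follow the words. If QTc was intended, limb (b) still has to be edited.

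**The repeats are not strictly mandatory, and other safeguards exist.** Both points stand. The over-read can waive a repeat. A reader might infer that QTcF above 500 ms would go unnoticed, but the documents do not support that. Site staff must compare each ECG with baseline. Every value in the window exceeds the Appendix 8 levels of 480 ms (may be an AE) and 500 ms (may be an SAE), and that appendix recommends core-laboratory alerts. Medically indicated supplemental measurements follow a recorded AE (10.3.3), unscheduled measurements are allowed (8.3), and limb (c) covers progressive lengthening. These safeguards are discretionary, concern reporting, or need serial ECGs. What is missing is only the automatic repeat.

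**Judging a QT alert on QTcF might look like a second error.** At 50 bpm, a QT of 500 to about 531 ms fires limb (b) but would fail confirmation if 500 ms is applied to QTcF. The documents do not make this an error. The section does not say outright which threshold applies to QTcF after a QT trigger, the two repeats are still taken, and rate-correcting an alert at a slow heart rate is reasonable. Escalating on raw QT has its own cost: QT 500 ms at 45 bpm is QTcF 454.3 ms, within the Groups 2-4 entry limit, and could lead to hourly ECGs and a cardiology consult without any QTcF concern.

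**Conclusion.** The point holds as a wording gap in the repeat-ECG rule. With limb (b) read as uncorrected QT, a post-dose QTcF above 500 ms calls for no protocol-required repeat when baseline exceeds 440 ms, the rise is under 60 ms and heart rate is above roughly 60 to 71 bpm, depending on the value.

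Exposure is low. All three conditions must coincide, and the documents give no frequency for them. Dosing is single. Table 1, whose columns are partly broken, appears to schedule only two post-dose ECGs, on Days 2 and 6, plus early termination. The first-in-human study showed no adverse clinically significant ECG changes (2.3.1).

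The ranges assume that the Day 1 predose baseline does not exceed the screening ceiling. A higher Day 1 value would widen them. How a QT alert at a slow heart rate is confirmed and escalated is a clinical choice for the sponsor to state.

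**What to change.** In both paragraphs of 8.3.3 (repeat ECGs and continuous monitoring), add an absolute QTcF of at least 500 ms as a trigger. Confirm, stop and escalate it on QTcF. The value matches the existing QT limit.

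Keep limb (b) on QT as an initial trigger for the two repeat ECGs. Replacing it with QTcF would drop cases such as QT 510 ms at 50 bpm (QTcF 479.9 ms). State which interval and which threshold confirms a limb (b) alert, and on which it is escalated. Keep limb (c). The 9.3.3.1 tabulations need no change.

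The cost is protocol wording in two paragraphs and possibly a few extra repeat ECGs. The ECG machines already report both intervals, and no existing trigger is removed. If the sponsor chooses to escalate limb (b) on raw QT, the burden on participants with slow heart rates would be larger and should be weighed first.
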